4.0 Patient Eligibility

4.1 Inclusion Criteria

Each patient must meet all the following inclusion criteria to be enrolled in the study:

1. Patient must have had relapsed disease prior to transplant, or undergone previous ASCT, followed by relapse and at least a partial response to salvage therapy.
2. Eligible patients will be enrolled in the protocol no less than 60 days and must be initiated no longer than 180 (+/- 14) days post ASCT.
3. Male or female patients 18 years or older.

4. Patients must have an Eastern Cooperative Oncology Group (ECOG) status of 0 to 2.
5. Patients' clinical laboratory values and toxicity must be as specified below within 14 days before the first dose of the study drug:
 - Platelet count $\geq 50,000/\text{mm}^3$
 - Absolute neutrophil count $\geq 1000/\text{mm}^3$ (no growth factors within 5 days)
 - Alanine aminotransferase (ALT) and aspartate aminotransferase (AST) $\leq 3 \times \text{ULN}$
 - Creatinine $\leq 2.5 \text{ mg/dL}$
 - Recovered (i.e., \leq grade 2 toxicity) from the reversible effects of autologous stem cell transplant.
6. Voluntary written informed consent before performance of any study-related procedure not part of normal medical care must be obtained, with the understanding that consent may be withdrawn by the subject at any time without any prejudice to future medical care.
7. Left ventricular ejection fraction $\geq 40\%$ (at the patient's last recorded echocardiogram (this could refer to pretransplant ECHO. ECHO may be repeated if the PI considers a repeat ECHO) No uncontrolled arrhythmias.

4.2 Exclusion Criteria

Patients meeting any of the following exclusion criteria are not to be enrolled in the study:

1. Major surgery within 14 days before the first dose of study drug.
2. Radiotherapy within 14 days before enrollment.
3. Non-secretory disease, plasma cell leukemia, or previous allogeneic transplant.
4. Known active central nervous system involvement.
5. Inability or unwillingness to comply with the drug administration requirements.
6. Female subject is pregnant or lactating.
7. Seropositive for human immunodeficiency virus (HIV).
8. Seropositive for hepatitis B (defined by a positive test for hepatitis B surface antigen [HBsAg]). Subjects with resolved infection (ie, subjects who are HBsAg negative but positive for antibodies to hepatitis B core antigen [anti-HBc] and/or antibodies to hepatitis B surface antigen [anti-HBs]) must be screened using real-time polymerase chain reaction (PCR) measurement of hepatitis B virus (HBV) DNA levels. Those who are PCR positive will be excluded. EXCEPTION: Subjects with serologic findings suggestive of HBV vaccination (anti-HBs positivity as the only serologic marker) AND a known history of prior HBV vaccination, do not need to be tested for HBV DNA by PCR.
9. Seropositive for hepatitis C (except in the setting of a sustained virologic response [SVR], defined as aviremia at least 12 weeks after completion of antiviral therapy).

10. Patients with a known history of asthma or chronic obstructive pulmonary disease with a forced expiratory volume in 1 second (FEV1) <50% of predicted normal.
11. Patients with moderate or severe persistent asthma within the past 2 years and currently uncontrolled asthma of any classification.
12. Infection requiring IV systemic antibiotic therapy within 7 days before C1D1 of therapy.
13. Known allergy to any of the study medications, their analogues, or excipients in the various formulations.
14. Failure to have fully recovered (i.e., <= grade 2 toxicity) from the effects of prior chemotherapy regardless of the interval since last treatment.
15. Patient is refractory or resistant to daratumumab and pomalidomide.
16. Co-morbid systemic illnesses or other severe concurrent disease that, in the judgment of the investigator, would make the patient inappropriate for entry into this study or interfere significantly with the proper assessment of safety and toxicity of the prescribed regimens.
17. If patient was unable to tolerate daratumumab or pomalidomide in the past.

5.0 Treatment Plan

5.1 Overall Design and Plan of Study

This will be a single arm, open label phase II, single center study of maintenance therapy with daratumumab/hyaluronidase-fihj and pomalidomide post salvage ASCT in patients with multiple myeloma.

The total number of patients to be treated in this study is 56 evaluable patients.

Patients should complete 2 cycles of therapy to be evaluable. For patients who receive fewer than 2 cycles due to progressive disease will be considered evaluable. Patient who received < 2 cycles due to AEs will be inevaluable for efficacy (response). All the other analysis will be conducted using intention to treat dataset.

Patients will have standard restaging studies prior to initiation of therapy. Standard post transplant therapy per institutional guidelines will be unaltered including prophylactic antibiotics, vaccinations and restaging.

Each cycle will be defined as a 28 day cycle. Drug holidays and break in therapy including those due to holidays, physician discretion and drug delivery are allowed as needed.

5.2 Daratumumab 1800 mg/hyaluronidase-fihj 30,000 units will be given SC weekly for weeks 1-8, followed by every 2 weeks for weeks 9-24, and then every month for weeks 25 until progression. On day 1 of each cycle, doses may be held if clinically indicated (i.e., active infections) for up to 4 weeks. If longer than 4 weeks, the PI will

evaluate and determine if the patient can continue on trial or must be taken off study. After day 1 of each cycle, subsequent doses may be held/skipped if clinically indicated (i.e., active infections) per PI or treating physician's discretion.

If daratumumab administration does not commence within the specified window (Appendix A), then the dose will be considered a missed dose. Administration may resume at the next planned dosing date. A missed dose will not be made up. Any adverse event deemed to be related to daratumumab that requires a dose hold of more than 28 days will result in permanent discontinuation of daratumumab. Subjects who miss ≥ 3 consecutive planned doses of daratumumab for reasons other than toxicity will be withdrawn from treatment, unless, upon consultation with the sponsor and review of safety and efficacy, continuation is agreed upon.

Subjects will receive pre-injection medications and post-injection medication as outlined in [Sections 3.1.3](#) and [3.1.4](#) respectively. See [Section 3.1.5](#) for instructions on the management of IRR and local ISRs.

5.3 Pomalidomide will be given at 2 mg PO daily from day 1-21 in the 28-day cycle. On day 1 of each cycle, doses may be held if clinically indicated (i.e., active infections) for up to 4 weeks. If longer than 4 weeks, the PI will evaluate and determine if the patient can continue on trial or must be taken off study. After day 1 of each cycle, subsequent doses may be held/skipped if clinically indicated (i.e., active infections) per PI or treating physician's discretion.

Pomalidomide not administered between days 1-21 in the 28 days cycle will be considered a missed dose. Administration may resume after active infection is resolved per PI or treating physician discretion. See section 3.2 for further instructions on toxicity management.

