8.6 Pregnancy

All initial reports of pregnancy must be reported to J&J by the Principal Investigator within 24 hours of becoming aware of the event using the Serious Adverse Event Form. Abnormal pregnancy outcomes (e.g., spontaneous abortion, fetal death, stillbirth, congenital anomaly, ectopic pregnancy) are considered serious adverse events and must be reported using the Serious Adverse Event Form.

Any subject who becomes pregnant during the study must be promptly withdrawn from the study and discontinue further study treatment.

Because the effect of the J&J medicinal product on sperm is unknown, pregnancies in partners of male subjects exposed to a J&J medicinal product will be reported by the Principal Investigator within 24 hours of their knowledge of the event using the Serious Adverse Event Form. Depending on local legislation this may require prior consent of the partner.

Follow-up information regarding the outcome of the pregnancy and any postnatal sequelae in the infant will be required.

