Note: Study drug is defined as daratumumab and pomalidomide.																			
a) To occur within 7 days after discontinuation of all study treatment.																			
b) In the 90 (+3) days after the last dose of daratumumab for safety follow-up visits. For subjects who discontinue study treatment before PD, disease evaluations should continue to be performed at the frequency specified below until confirmed PD, death, start of a new anticancer treatment, withdrawal of consent to study participation, or end of the study, whichever occurs first. Once PD is confirmed, subsequent disease evaluation time points are not required.																			
- Every 8-12 weeks (± 3 days), at clinician's discretion: SPEP and 24-hour UPEP assessments, and serum calcium corrected for albumin																			
- Every 4 weeks (± 3 days), or at clinician's discretion: physical examination of extramedullary plasmacytomas if applicable																			
- Every 12 weeks (± 14 days), or at clinician's discretion: radiologic imaging of extramedullary plasmacytomas if applicable																			
- When CR is suspected or maintained: serum FLC, serum and urine immunofixation																			
- As clinically indicated: skeletal survey																			

- Evidence of clinical relapse will also be documented at the time at which it is first detected.

After PD is determined, patient will be taken off study and no further study evaluations will be needed.

- c) Blood pressure is to be measured at the following time points on Cycle 1 Days 1: immediately pre-administration, at the end of administration, 30 minutes post administration, 60 minutes post administration, and then hourly until 6 hours post administration. On Cycle 1 Day 8: immediately pre-administration, at the end of administration, 30 minutes post administration, 60 minutes post administration, and 120 minutes post administration. On Cycle 1 Day 15 onward: immediately pre-administration, at the end of administration, 15 minutes post administration. Infusion observation times and vital signs may be adjusted per PI discretion.
- d) Pre-infusion medications to be given before all daratumumab infusions (if necessary, oral pre-infusion medications may be administered at the subject's home on the day of the infusion, provided they are given within 3 hours prior to the infusion)
- e) Unless otherwise stated, all blood and urine samples must be obtained before administration of study treatment.

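### After a hold of more than 4 weeks, 5.2 and 5.3 let the PI take a patient off study, while Appendix A footnote b keeps patients who stop treatment in follow-up; read literally, the hold rule censors PFS early and could bias it

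*Combined protocol and SAP*

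**What the plan says.** Section 5.3 (pomalidomide) allows that "doses may be held if clinically indicated (i.e., active infections) for up to 4 weeks", and then: "If longer than 4 weeks, the PI will evaluate and determine if the patient can continue on trial or must be taken off study". Section 5.2 (daratumumab) has the same rule: the PI will "evaluate and determine if the patient can continue on trial or must be taken off study". The next paragraph of 5.2 uses a different term for missed doses. Patients who miss three or more consecutive "planned doses of daratumumab for reasons other than toxicity will be withdrawn from treatment", unless continuation is agreed.

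Appendix A footnote b covers what happens after treatment stops: "For subjects who discontinue study treatment before PD, disease evaluations should continue to be performed at the frequency specified below until confirmed PD", or until "death, start of a new anticancer treatment, withdrawal of consent to study participation, or end of the study, whichever occurs first". A PI decision after a long hold is not among these end points. The same footnote shows what off study means in this protocol: "After PD is determined, patient will be taken off study and no further study evaluations will be needed".

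Section 7.3 censors patients who are alive and progression-free at their last follow-up. Section 5.1 puts all analyses other than response on an intention-to-treat basis. Section 7.2 places the remission assessment 6 months into maintenance. Section 8.6 says that a patient who becomes pregnant "must be promptly withdrawn from the study and discontinue further study treatment", and then asks for follow-up of the pregnancy outcome.

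**The concern.** Leaving treatment and leaving the study are different events for the analysis. A patient who stops treatment but stays in follow-up still contributes a progression or death date to PFS. A patient taken off study contributes only time up to removal.

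Kaplan-Meier assumes that censored patients have the same later risk as those still followed. The protocol's example of a reason for a hold is active infection, and PFS counts death from any cause. It is therefore plausible, though not shown, that a patient whose hold exceeds 4 weeks has a higher event hazard. If so, censoring at removal makes PFS look longer; if not, it only costs events. Closing patients out before progression also sits badly with the intention-to-treat statement.

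For response, a patient removed after two cycles but before month 6 remains evaluable under 5.1 and may have no scheduled CR assessment. No rule says how that patient counts. Counted as a non-remission, the rate falls; dropped from the denominator, it could rise. PFS and CRR are the two efficacy endpoints, so the point matters whichever is primary (1.1 names CRR, 7.1 names PFS).

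**Working it through.** **1. The texts side by side.**
- 5.2 and 5.3, hold over 4 weeks: continue on trial, or off study.
- 5.2, related adverse event needing a hold over 28 days: daratumumab permanently discontinued (treatment wording).
- 5.2, three or more missed doses for reasons other than toxicity: withdrawn from treatment (treatment wording).
- 5.7, maximum delay: treatment discontinued (treatment wording).
- Footnote b: evaluations go on after treatment stops; off study means they end.

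The protocol thus separates the two states elsewhere, and the 4-week rule in 5.2 and 5.3 uses the one that ends evaluation.

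**2. The plan's own figures (7.1).** Inputs: medians 12 and 20 months, 56 patients, 36 months' accrual, 60 months' maximum follow-up, two-sided 0.05, exponential survival.
- L = ln 2/20. Expected events = 56 × [1 − (e^(−24L) − e^(−60L))/(36L)] = 56 × [1 − (0.4353 − 0.1250)/1.2477] = 56 × 0.7513 = 42.07. The plan says 42.
- Power = Φ(√42 × |ln(12/20)| − 1.96) = 0.912. The plan says 0.91.

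Both reproduce, on the premise that nobody is lost early.

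**3. Events lost, equal hazard.** Assumptions, not in the documents: a share q is removed, at a time uniform over months 2 to 12.
- Chance of an event before removal = 1 − (e^(−2L) − e^(−12L))/(10L) = 0.2115, against 0.7513 if followed.
- Events lost = 56 × q × (0.7513 − 0.2115) = 30.2q.

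| q | Events | Power at that count |
|---|---|---|
| 0 | 42.1 | 0.91 |
| 5% | 40.6 | 0.90 |
| 10% | 39.0 | 0.89 |
| 20% | 36.0 | 0.87 |

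The Kaplan-Meier median stays at 20.0 months throughout.

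**4. Median PFS when removal is linked to risk.** The others keep hazard L; removed patients have k times L. The true median solves (1 − q)e^(−Lt) + q·e^(−kLt) = 0.5. The censored reading is the large-sample Kaplan-Meier median, which averages the hazards over patients still at risk, with removed patients leaving over months 2 to 12.

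| k | q | True median | Read as | Excess | Events, followed → censored |
|---|---|---|---|---|---|
| 1 | any | 20.0 | 20.0 | 0 | as in step 3 |
| 2 | 5% | 19.3 | 19.7 | 0.4 | 42.6 → 41.0 |
| 2 | 10% | 18.6 | 19.4 | 0.8 | 43.1 → 39.9 |
| 2 | 20% | 17.3 | 18.7 | 1.4 | 44.1 → 37.8 |
| 3 | 20% | 15.9 | 17.7 | 1.8 | 44.6 → 39.2 |

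**5. A second set-up.** Here the overall true median is held fixed and removal is uniform over months 0 to 12. For a true 20 months and k = 2, the median reads 20.5, 20.9 or 21.9 at 5%, 10% or 20% removed. With a true median of 12 months, q = 10% and k = 2, the simulated chance of wrongly rejecting in the favourable direction (nominal 0.025) is 0.042 with censoring, against 0.025 with follow-up.

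**The case against.** The strongest reply is that the text does not close anyone out automatically. The PI decides case by case, at a single center, and may read off study as off treatment, in which case footnote b applies and nothing is lost. Many long holds also fall under rules that already use treatment wording, and 5.1 allows breaks in therapy as needed, so few patients may be affected. This stands as a limit on size. It does not remove the conflict, because footnote b itself uses off study to mean no further evaluations.

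A reader might infer more than the documents support:
- *That PFS is overstated.* This holds only if removed patients have a higher hazard. At ratio 1 there is no bias.
- *That the removed patients are those doing badly.* The text names only active infections, not worsening myeloma.
- *That CR data are lost.* Section 6.2 stages patients every 3 cycles, and Appendix A calls for marrow to confirm CR, so a remission documented before removal could still count. The scheduled 6-month assessment is what may be missed.

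The shifts are also small against sampling error. With 42 events, an approximate 95% interval around 20 months is 20 × e^(±1.96/√42), or 14.8 to 27.1. That is a fair point about size, but sampling error is reported with the estimate and this bias would not be.

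Section 8.6 adds little: it already asks for pregnancy-outcome follow-up, and no number of pregnancies is given.

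**Conclusion.** The conflict between 5.2/5.3 and footnote b is real and should be resolved. Applied literally, the hold rule ends PFS follow-up before progression for some patients, and 7.3 then censors them. The firm consequence is lost events: about 1.5, 3 or 6 of 42 at 5%, 10% or 20% removed with equal hazard. The conditional one is a median overstated by about 0.4, 0.8 or 1.4 months at a hazard ratio of 2, with none at a ratio of 1. The removal share, its timing and the hazard ratio are all assumptions. The expected effect is modest, but follow-up that was not collected cannot be recovered at analysis.

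**What to change.** In 5.2 and 5.3, replace *taken off study* with: *taken off study treatment; disease evaluations continue per Appendix A footnote b*. Keep *off study* for the end points listed in footnote b and for loss to follow-up. As a minor consistency edit, change 8.6 in the same way, so that the patient is withdrawn from study treatment and follow-up continues.

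The PI's decision on whether to stop treatment, and the hold length, are unchanged. The cost is wording in three places and, for a few patients, follow-up that footnote b already plans. The edit does not settle how a missing 6-month CR assessment is counted; that needs its own sentence in 7.3.

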5.4 Prophylaxis for herpes zoster reactivation

Initiate antiviral prophylaxis to prevent herpes zoster reactivation within 1 week of starting daratumumab and continue for 3 months following treatment.

5.5 Dose Delay

Before each cycle, the patient will be evaluated for possible toxicities that may have occurred after the previous dose(s). Toxicities are to be assessed according to the NCI Common Toxicity Criteria for Adverse Events (CTCAE), version 4.0 (<http://ctep.cancer.gov/reporting/ctc.html>). Each AE should be attributed to a specific drug, if possible, so that the dose modifications can be made accordingly. If multiple toxicities are noted, the dose delays are per PI discretion; refer to guidelines that address the most severe toxicity.

5.6 Criteria for beginning a subsequent treatment cycle

Treatment with daratumumab will use a cycle length of 28 days. For a new cycle of treatment to begin, the patient must meet the following criteria:

- ANC must be $\geq 1,000/\text{mm}^3$
- Platelet count must be $\geq 50,000/\text{mm}^3$

In addition, all other toxicity considered to be related to treatment must have resolved to \leq grade 1, to the patient's baseline values, or to a level considered acceptable by the physician (e.g., hypokalemia that can be managed by replacements) before a new cycle of treatment may begin.

5.7 Criteria for delaying a subsequent treatment cycle

If the patient fails to meet the above-cited criteria for initiation of the next cycle of treatment or has any of the below toxicities, dosing should be delayed until recovery.

- Grade 4 hematologic toxicities
- Grade 3 thrombocytopenia with bleeding
- Febrile neutropenia of any grade
- Neutropenia with infection, of any grade
- Grade 3 or higher nonhematologic toxicities with the following exceptions:
 - Grade 3 nausea that responds to antiemetic treatment within 7 days
 - Grade 3 vomiting that responds to antiemetic treatment within 7 days
 - Grade 3 diarrhea that responds to antidiarrheal treatment within 7 days
 - Grade 3 fatigue that was present at baseline or that lasts for <7 days after the last administration of daratumumab
 - Grade 3 asthenia that was present at baseline or that lasts for <7 days after the last administration of daratumumab

The maximum delay before treatment should be discontinued is 6 weeks or at the discretion of the Principal Investigator.

5.8 Management of Clinical Event

5.8.1 Nausea and/or Vomiting

Standard anti-emetics, including 5-HT₃ antagonists, are recommended for emesis occurring upon treatment initiation; prophylactic anti-emetics may also be considered. Dexamethasone should not be administered as an anti-emetic. Fluid deficits should be corrected before initiation of study drug and during treatment.

5.8.2 Diarrhea

Diarrhea should be managed according to clinical practice, including administration of antidiarrheal therapy once infectious causes are excluded. Fluid intake should be maintained to avoid dehydration. Fluid deficits should be corrected before initiation of treatment and during treatment.

5.8.3 Thrombocytopenia

Thrombocytopenia has been reported with daratumumab. Blood counts should be monitored regularly as outlined in the protocol with additional testing obtained according to standard clinical practice. Thrombocytopenia may be severe but has been managed with platelet transfusions according to standard clinical practice.

5.8.4 Neutropenia

Neutropenia has been reported with daratumumab. Blood counts should be monitored regularly as outlined in the protocol with additional testing obtained according to standard clinical practice. Neutropenia may be severe but has been managed with G-CSF according to standard clinical practice.

5.9 Concomitant Treatment

Permitted Concomitant Medications and Procedures

All necessary supportive care consistent with optimal patient care shall be available to patients as necessary. Radiotherapy is permitted to palliate symptoms during maintenance therapy. The following are examples of those permitted during the study:

- Growth factors (e.g., granulocyte colony stimulating factor (G-CSF), granulocyte macrophage-colony stimulating factor (GM-CSF), recombinant erythropoietin).
- Red cell and platelet transfusions as clinically indicated
- Prophylactic antibiotics for pneumocystis (i.e., Bactrim) needed post ASCT
- Antiviral prophylaxis (i.e., Valtrex) is recommended for all patients to prevent HSV or zoster
- Bisphosphonate therapy
- Medications for neuropathy as needed at the discretion of the investigator.

Prohibited Concurrent Therapy

Other anti-myeloma directed systemic therapy

